1.5 Sensitizing Glioblastoma to Temozolomide

Currently, temozolomide represents the only systemic therapy that has been shown to improve OS for glioblastoma (Stupp, et al. 2005). A phase II study attempted to re-sensitize recurrent temozolomide-resistant glioblastoma (those who would recur while receiving temozolomide or within 2 months of the last treatment of temozolomide) using an O⁶-methylguanine-DNA methyltransferase (MGMT) inhibitor called O⁶-benzylguanine (OBG) (Quinn, et al. 2009). Since MGMT is an enzyme that repairs DNA damage by alkylating agents such as temozolomide, a MGMT inhibitor is thought to be a rational agent to re-sensitize glioblastoma to temozolomide. Unfortunately, combination of O⁶-benzylguanine and temozolomide did not show any evidence of significant re-sensitization: ORR of 3% (95% CI: 0-15%), PFS6 of 9% (95% CI: 2-21%), and median PFS of 7.5 weeks (95% CI: 4.2-7.9 weeks) (Quinn, et al. 2009).

[figure not shown]

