10.0 STATISTICAL CONSIDERATIONS

10.1 Definition of Primary Endpoints and Analytical Plan

The co-primary endpoints will be ORR and PFS6. ORR will be defined as the percentage of patients with CR or PR according to the RANO criteria as described in Section 6.0. PFS6 will be defined as proportion of patients that are free from progressive disease (PD) as per RANO criteria or death at 6 months from the date of the first dose of DSF-Cu. PFS6 and median PFS will be estimated using the Kaplan-Meier product-limit method. For unmethylated glioblastoma receiving temozolomide without DSF-Cu, an ORR of less than 10% and PFS6 of less than 20% (Quinn, et al. 2009).

To justify future use of or drug development of DSF-Cu for glioblastoma, we hypothesized that the addition of DSF-Cu to temozolomide would improve ORR to 20% or increase PFS6 to 30%. The sample size is calculated based on the above hypotheses with one-sided exact test at an approximate α level of 0.10 and 80% statistical power. At these type I and II error rates, 14 -20 patients will detect a proportion of patients who have ORR significantly higher than 5% or PFS6 significantly higher than 10%. Of note, previous phase II study testing addition of O⁶-benzylguanine (a MGMT inhibitor) to temozolomide for temozolomide-resistant glioblastoma used similar hypothesis and observed a disappointing ORR of 3% and PFS6 of 9% (Quinn, et al. 2009). This negative phase II study has detailed information on ORR, PFS, and OS as well as associated estimated 95% CIs and will serve as a historical comparison for this study.

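### Section 10.1 ties 14-20 patients to unexplained nulls of 5% ORR and 10% PFS6, and its alpha and power pair does not hold up to the 10% and 20% bounds it gives for treatment without DSF-Cu

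*Combined protocol and SAP*

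**What the plan says.** All the figures in question stand in Section 10.1 of the combined protocol and SAP.

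- Rates for unmethylated glioblastoma on temozolomide "without DSF-Cu, an ORR of less than 10% and PFS6 of less than 20" per cent.
- Targets: adding DSF-Cu "would improve ORR to 20% or increase PFS6 to 30" per cent.
- Basis of the size: "The sample size is calculated based on the above hypotheses".
- Test: "one-sided exact test at an approximate α level of 0.10 and 80% statistical power".
- Result: "14 -20 patients will detect a proportion of patients who have ORR significantly higher than 5% or PFS6 significantly higher than 10" per cent.

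The same section names an earlier phase II study of an MGMT inhibitor plus temozolomide as the historical comparison and reports that it "observed a disappointing ORR of 3% and PFS6 of 9" per cent. Section 1.5 gives that study's intervals: "ORR of 3% (95% CI: 0-15%), PFS6 of 9% (95% CI: 2-21" per cent. Section 3.0 plans about 14 to 40 patients, with possible closure at 14-20 after a look at 14. Section 4.0 describes a single-arm study.

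**The concern.** The nulls in the sample-size sentence are half the bounds given a few lines earlier. They are not among the hypotheses the size is said to rest on, and no section explains where they come from. The nearest figures are the historical study's point estimates of 3% and 9%, whose printed upper limits reach 15% and 21%.

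The trial has no control arm, so the null rate is its only comparator. Rejecting 5% ORR does not exclude 6% to 10%, and rejecting 10% PFS6 does not exclude 11% to 20%. Both ranges are within or at the edge of what Section 10.1 allows for treatment without DSF-Cu. The result is meant to support further development, and a reader would take a success to mean that the regimen beat the quoted reference at a 10% error rate. That is not what the test delivers.

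**Working it through.** **Inputs, all from Section 10.1 unless noted:** one-sided exact test, alpha about 0.10, power 80%; bounds without DSF-Cu of 10% (ORR) and 20% (PFS6); targets 20% and 30%; nulls 5% and 10%; n=14-20, and 40 as the upper enrolment figure in Section 3.0.

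**Assumptions.** No cut-off is printed, so I take r as the smallest count with P(X ≥ r | n, p0) ≤ 0.10, where X is binomial(n, p). PFS6 is treated as a simple proportion with every patient's six-month status known. All figures are per endpoint.

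**Step 1: reproduce the plan's size with nulls 5% and 10%.**
- ORR 5% v 20%: n=20, r=3 gives alpha 0.075 and power 0.794. Power first reaches 80% at n=21 (alpha 0.085, power 0.821).
- PFS6 10% v 30%: power first reaches 80% at n=18, r=4 (alpha 0.098, power 0.835). At n=20, r=5, alpha is 0.043 and power 0.762.
- The normal approximation n = [(1.2816√(p0(1−p0)) + 0.8416√(p1(1−p1)))/(p1−p0)]² gives (0.6160/0.15)² = 16.9, so 17, for ORR and (0.7702/0.20)² = 14.8, so 15, for PFS6.

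The 14-20 range therefore reproduces towards its upper end, with 5% and 10% as the nulls. At n=14 the exact power is only 0.552 and 0.645.

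**Step 2: keep those cut-offs and set the true rates at the section's own bounds.**

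| n | ORR cut-off | P(success), true ORR 10% | PFS6 cut-off | P(success), true PFS6 20% |
|---|---|---|---|---|
| 14 | ≥3 | 0.158 | ≥4 | 0.302 |
| 16 | ≥3 | 0.211 | ≥4 | 0.402 |
| 18 | ≥3 | 0.266 | ≥4 | 0.499 |
| 20 | ≥3 | 0.323 | ≥5 | 0.370 |

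Below the bound the probability falls. At n=20 it is 0.115 for a true ORR of 6%, and 0.095 and 0.170 for a true PFS6 of 12.5% and 15%. At the historical study's 3% and 9% it is 0.021 and 0.029.

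**Step 3: hold alpha at 0.10 or less against 10% and 20%, and find power at 20% and 30%.**

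| n | ORR cut-off | alpha | power | PFS6 cut-off | alpha | power |
|---|---|---|---|---|---|---|
| 14 | ≥4 | 0.044 | 0.302 | ≥6 | 0.044 | 0.220 |
| 16 | ≥4 | 0.068 | 0.402 | ≥6 | 0.082 | 0.340 |
| 18 | ≥4 | 0.098 | 0.499 | ≥7 | 0.051 | 0.278 |
| 20 | ≥5 | 0.043 | 0.370 | ≥7 | 0.087 | 0.392 |
| 40 | ≥7 | 0.099 | 0.714 | ≥12 | 0.087 | 0.559 |

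Power first reaches 80% at n=61 for ORR (r=10, alpha 0.080, power 0.804) and n=88 for PFS6 (r=23, alpha 0.098, power 0.817).

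**Step 4: sensitivity to the word approximate.** One cut-off lower at n=20 gives ORR ≥4 with alpha 0.133 and power 0.589, and PFS6 ≥6 with alpha 0.196 and power 0.584. A looser reading of alpha does not recover 80% either.

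**The case against.** The strongest reply is that 10% and 20% are ceilings, not rates. A null of 5% is below 10%, a null of 10% is below 20%, and both sit just above the 3% and 9% of the study named as the historical comparison. The sentence giving the bounds is also grammatically incomplete, so its intended role is uncertain. This stands to the extent that there is no literal contradiction. It does not supply the missing link: nothing in the section says that 5% and 10% were chosen for that reason, and a type I error claimed against a rate described only as below 10% or 20% has to hold up to that limit.

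Three stronger readings are tempting, and the documents do not support them.

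- A reader might infer that any ineffective regimen has about a one-in-three chance of success. That applies at the bound. At 3% and 9% the chance is 2% to 3% at n=20.
- A reader might infer that the trial lacks power at its targets in every sense. Under the 5%/10% cut-offs, power at 20%/30% is 0.79 and 0.76 at n=20, close to what is stated.
- A reader might infer that power against 10%/20% is always less than half of 80%. For ORR it is 0.40 to 0.50 at n=16 to 18. The 0.37 at n=20 partly reflects the discreteness of the test, since the cut-off there spends only 0.043.

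It is also fair to say that Section 3.0 allows up to 40 patients. That raises power against 10%/20% to 0.71 and 0.56, still short of 0.80.

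**Conclusion.** The point holds as an unexplained mismatch between the reference bounds and the tested nulls, not as an arithmetic slip. What fails is alpha and power taken together. With the 5%/10% nulls, power is near 80% at n=20, but the error at the bounds is 0.16-0.32 for ORR and 0.30-0.50 for PFS6 over n=14-20. With the bounds as nulls, alpha is controlled, but power is 0.30-0.50 and 0.22-0.39. No n from 14 to 20 gives alpha 0.10 and power 80% for 10% v 20% or 20% v 30%.

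These sizes rest on the assumed cut-off rule and on complete six-month status. The conclusion does not depend on whether the historical study's population suits this trial, which is a separate question. It should be corrected before analysis because it concerns the primary decision rule.

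**What to change.** In Section 10.1, state and justify one null rate per endpoint, print the success cut-off, and give the actual alpha and power for the n used. Two versions are workable.

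1. Test against 10% and 20%. At n=20 success is at least 5/20 responders (alpha 0.043, power 0.37 at 20%) or at least 7/20 progression-free at six months (alpha 0.087, power 0.39 at 30%). The 80% claim is withdrawn.
2. Keep 5% and 10% with a stated justification, and remove the below-10% and below-20% figures as the reference. At n=20 the cut-offs are 3/20 and 5/20, with alpha 0.075 and 0.043 and power 0.79 and 0.76. State that success excludes only 5% and 10%, and would occur up to 32% and 37% of the time if the true rates were as high as 10% and 20%.

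If accrual ends at another n, the cut-off, alpha and power for that n should be given in the same way. Either version costs only wording and a less favourable stated figure; no extra patients are needed. Keeping 80% power against 10%/20% would be a different choice, needing 61 and 88 patients, beyond the 40 in Section 3.0.

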10.2 Definition of Secondary Endpoints and Analytical Plans

The secondary endpoints will be toxicity, and OS.

1. Toxicities that are possibly/probably/definitively related to DSF will be graded by NCI CTCAE version 4.0 (2009) and will be tabulated by type and grade.
2. OS will be measured from the date of the first dose of DSF+Cu to the date of death or, otherwise, the last follow-up date on which the patient was reported alive. Median OS and OS12 (proportion of patients that are alive at 12 months) will be estimated using the Kaplan-Meier product-limit method.

APPENDIX A:

GRADE	ECOG PERFORMANCE STATUS
0	Fully active, able to carry on all pre-disease performance without restriction
1	Restricted in physically strenuous activity but ambulatory and able to carry out work of a light or sedentary nature, e.g., light house work, office work
2	Ambulatory and capable of all selfcare but unable to carry out any work activities; up and about more than 50% of waking hours
3	Capable of only limited selfcare; confined to bed or chair more than 50% of waking hours
4	Completely disabled; cannot carry on any selfcare; totally confined to bed or chair
5	Dead

APPENDIX B – Comparison of the ECOG Performance Status to the Karnofsky Performance Status

ECOG PERFORMANCE STATUS	KARNOFSKY PERFORMANCE STATUS
0—Fully active, able to carry on all pre-disease performance without restriction	100—Normal, no complaints; no evidence of disease
1—Restricted in physically strenuous activity but ambulatory and able to carry out work of a light or sedentary nature, e.g., light house work, office work	90—Able to carry on normal activity; minor signs or symptoms of disease 80—Normal activity with effort, some signs or symptoms of disease
2—Ambulatory and capable of all selfcare but unable to carry out any work activities; up and about more than 50% of waking hours	70—Cares for self but unable to carry on normal activity or to do active work 60—Requires occasional assistance but is able to care for most of personal needs
3—Capable of only limited selfcare; confined to bed or chair more than 50% of waking hours	50—Requires considerable assistance and frequent medical care 40—Disabled; requires special care and assistance
4—Completely disabled; cannot carry on any selfcare; totally confined to bed or chair	30—Severely disabled; hospitalization is indicated although death not imminent 20—Very ill; hospitalization and active supportive care necessary
5—Dead	10—Moribund 0—Dead

APPENDIX C: Disulfiram and Copper Medication Diary

Today's Date: _____ Agent: Disulfiram/Copper Month: _____

Patient Name: _____

INSTRUCTIONS TO THE PATIENT:

1. Complete one form for each month. Take ___ mg (___capsule) of disulfiram two times a day with meals with breakfast and dinner). Please also take 2 mg of copper gluconate supplement two times a day with each meal. Do **not** take disulfiram or copper within one hour of your dose of temozolomide.
2. Record the date, and how many times you took disulfiram and copper on that date.
3. If you have any questions or notice any side effects, please record them in the comments section. Record the time if you should vomit.
4. Please return the forms to your physician or your study coordinator when you go to your next appointment. Please bring your unused study medications and/or empty bottles with you to each clinic visit so that a pill count can be done.
5. Avoid consuming alcohol before and throughout the entire study.

Day	Date	Check each time you take your disulfiram dose			Check each time you take your copper dose			Comments
		Breakfast	Lunch	Dinner	Breakfast	Lunch	Dinner	
1								
2								
3								
4								
5								
6								
7								
8								
9								
10								
11								
12								
13								
14								
15								
16								
17								
18								
19								
20								
21								
22								
23								
24								
25								
26								
27								
28								

APPENDIX D: Concurrent Temozolomide Medication Diary

Today's Date: _____ Agent: Temozolomide Month: _____

Patient Name: _____

INSTRUCTIONS TO THE PATIENT:

1. **Complete this form. Take _____mg (___capsules) of temozolomide daily as instructed by your oncologist.** Temozolomide should be taken within one hour of your radiation appointment each day on an empty stomach and should not be taken within one hour of your disulfiram or copper supplement. During weekends without radiation treatments (Saturday and Sunday), temodar will be taken in the morning.
2. Record the date, the number of capsules taken, and when you took them.
3. If you forget to take temozolomide before midnight, then do not take a dose that day. Restart it the next day.
4. If you have any questions or notice any side effects, please record them in the comments section. Record the time if you should vomit.
5. Please return the forms to your physician or your study coordinator when you go to your next appointment. Please bring your unused study medications and/or empty bottles with you to each clinic visit so that a pill count can be done.
6. Avoid consuming alcohol before and throughout the entire study.

Day	Date	What time was dose taken?	# of tablets taken	Comments
1				
2				
3				
4				
5				
6				
7				
8				
9				
10				
11				
12				
13				
14				
15				
16				
17				
18				
19				
20				
21				
22				
23				
24				
25				
26				
27				
28				
29				

ANII 100-1 Clinical Study Protocol: DSF-Cu for Unmethylated Glioblastoma

30				
31				
32				
33				
34				
35				
36				
37				
38				
39				
40				
41				
42				

APPENDIX E: Adjuvant Temozolomide Medication Diary

Today's Date: _____ Agent: Temozolomide Month: _____

Patient Name: _____

INSTRUCTIONS TO THE PATIENT:

1. Complete this form. Take _____ mg (___ capsules) of temozolomide daily as instructed by your oncologist. **Temozolomide should be taken at bedtime on an empty stomach and should not be taken within one hour of your disulfiram or copper supplement.**
2. Record the date, the number of capsules taken, and when you took them.
3. If you forget to take temozolomide before midnight, then do not take a dose that day. Restart it the next day.
4. If you have any questions or notice any side effects, please record them in the comments section. Record the time if you should vomit.
5. Please return the forms to your physician or your study coordinator when you go to your next appointment. Please bring your unused study medications and/or empty bottles with you to each clinic visit so that a pill count can be done.
6. Avoid consuming alcohol before and throughout the entire study.

Day	Date	What time was dose taken?	# of tablets taken	Comments
1				
2				
3				
4				
5				
6				
7				
8				
9				
10				
11				
12				
13				
14				
15				
16				
17				
18				
19				
20				
21				
22				
23				
24				
25				
26				
27				
28
